**Step 2: Combination of events:**

Overlapping/consecutive events are defined as events of the same subject with the same preferred term which have at least 1 day overlap or for which the start date of an event is 1 day after the end date of the preceding event. Overlapping/consecutive events may be combined into one AE or not, according to the following rules:

1. If overlapping/consecutive events start in one of the following periods - Screening or follow up (i.e. non-active periods) - followed by an AE in a post-dose period (active period) - they are allocated to their respective periods and are considered as separate events.
2. In case overlapping/consecutive events start within a single period, they are considered as one and the same AE. The individual events which contribute to this AE are retained as individual records in the ADaM database but are assigned the same onset, period, and total duration. All related attributes to the AE/phase/period should also be consistent with the new event.
3. In case overlapping/consecutive events start in both an active period followed by a non-active period, they are allocated to the active period only and are considered as one and the same AE. The individual events which contribute to this AE are retained as individual records in the ADaM database but are assigned the same onset, treatment period, and total duration. All related attributes to the AE/phase/period should also be consistent with the new event.
4. In case an active period is followed by another active period, and the overlapping/consecutive events start in both periods, they are allocated to their respective period and are considered as separate AEs. In case overlapping/consecutive events start in non-consecutive periods (regardless of active or non-active), they are allocated to their respective period and are considered as separate AEs.
5. In case a non-active period is followed by another non-active period, and the overlapping/consecutive events start in both periods, they are allocated to the first period and they are considered as one and the same AE. The individual events which contribute to this AE are retained as individual records in the ADaM database but are assigned the same onset, period, and total duration. All related attributes to the AE/phase/period should also be consistent with the new event.

**Remarks:**

- Events can only be combined into one and the same AE if their start and stop dates are known.
- In case the completely missing end date is imputed (for period allocation), this date is also considered as a complete date.
- Time is not considered when determining overlap of events.

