##### **Step 1: Allocation of events to the periods:**

Adverse events in the SDTM database are allocated to periods based on their start date/time.

- If the start date/time of an event falls between (or on) the start and stop date/time of a period, the AE is attributed to that period (emergent principle).
- In case of partial start or stop dates (i.e. time and/or day and/or month and/or year missing), the events are allocated to the periods using the available partial information on start and end date; no imputation will be done. If, for instance, the AE start date only month and year are available, these data are compared to the month and year information of the periods. This rule may lead to multiplication of the event as a consequence of its assignment to multiple periods.
- In case of a completely missing end date, the date is imputed by the cut-off date of the analysis for subjects still ongoing in the study, and by the end date of the last phase for subjects who discontinued or completed the study.
- In case of a completely missing start date, the event is allocated to the first active treatment phase (post dose 1 period), except if the end date of the AE falls before the start of the first active treatment phase (post dose 1 period).

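### A later SAE can be re-dated into the 28-day post-dose period only because an earlier AE of the same term has no end date

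*SAP*

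**What the plan says.** All of this is in SAP Section 4.2.1.3.

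- **Step 1, imputation.** When an end date is completely missing, "the date is imputed by the cut-off date of the analysis for subjects still ongoing in the study". Participants who have left or finished are handled differently: their last phase supplies the imputed date.
- **Step 2, overlap.** Events are candidates for combining if they are "events of the same subject with the same preferred term which have at least 1 day overlap", or if one starts the day after the other ends. Seriousness, grade and outcome play no part.
- **Step 2, rule 3.** "In case overlapping/consecutive events start in both an active period followed by a non-active period, they are allocated to the active period only". The contributing records stay in ADaM but share one onset, period and total duration.
- **Step 2, rules 1 and 4.** Events stay separate when a non-active period is followed by an active one, when both periods are active, or when the periods are not consecutive.
- **Remarks.** The first sets a safeguard: "Events can only be combined into one and the same AE if their start and stop dates are known". The second makes an exception to it: "In case the completely missing end date is imputed (for period allocation), this date is also considered as a complete date".

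Section 5.2 applies the same steps to the AESI time intervals, with 0-28 days treated as active and the other intervals as non-active.

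**The concern.** The imputed end date lies at the end of the participant's available data. An AE with a blank end date therefore overlaps every later record of the same term by construction, whether or not the first event had resolved. Where rule 3 applies, the later record takes the earlier onset and the post-dose period. No condition protects a later serious event from being folded into an earlier non-serious one.

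The tables that carry this information exist to show timing relative to vaccination. Safety results are presented by period (Section 2.1), SAE tables are by period (Section 5.2), and the unsolicited AE tables cover the 28 days after vaccination and include SAEs and fatal outcomes (Sections 4.2.1.1 and 4.2.1.2). A merged late SAE would add a case to the 28-day window that did not begin there, and remove one from follow-up. After revaccination every recipient gets an active product (Table 1), so no concurrent placebo column would reveal it.

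**Working it through.** The SAP gives no figure to reproduce. The check applies the written rules to a test case; the event days are illustrative.

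**1. Dated example.**
- Vaccination on 1 October 2019 is Day 1.
- A non-serious AE starts on 10 October 2019: 9 days later, + 1 = Day 10. The end date is blank.
- An SAE of the same term starts on 1 March 2020: 31 + 30 + 31 + 31 + 29 = 152 days later, + 1 = Day 153.
- With a cut-off of 15 May 2020 (the date used in Section 4.4.2.1.3) and the participant ongoing, the imputed interval runs from 10 October 2019 to 15 May 2020 and covers the SAE.
- Day 10 is in the post-dose period (active; Table 2 ends it at the later of 28 days and the 4-week visit). Day 153 is in First Year Follow up (non-active, the next period). Rule 3 applies.
- Result: one AE in the post-dose period with onset Day 10. The SAE is dated 153 − 10 = 143 days early.

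**2. Reach by phase.** Index AE on day 10; second same-term event on the day shown; participant ongoing and not revaccinated.

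| Second event | Rule as written, end date blank | Index end known (day 15) | Imputed dates not accepted for combining |
|---|---|---|---|
| Day 40, 100, 200 or 350 | Rule 3: one AE, post-dose, onset day 10 | Separate, First Year Follow up | Separate, First Year Follow up |
| Day 380 or 500 | Rule 4: separate, second year | Separate, second year | Separate, second year |
| Day 800 | Rule 4: separate, third year | Separate, third year | Separate, third year |

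The first row shows that the blank end date alone causes the shift. For Subcohort A, a second event on day 380 falls after revaccination and also stays separate under rule 4.

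**3. Reach by AESI interval (Section 5.2).** A second event on day 40 (29-56 days) is merged into 0-28 days. On day 100 or later it is in a non-consecutive interval and stays separate, so the Day 153 example does not arise there. The one exception is the case Section 5.2 describes in which a late 4-week visit removes the 29-56 day interval; 57 days to 6 months is then the adjacent interval.

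**4. Limits on the length of the shift.** Merging can reach to the end of First Year Follow up, for instance day 350 − day 10 = 340 days, about 11 months. But Section 5.2 collects all SAEs after dose 1 only until the later of the end of the first season or 6 months after vaccination; after that only restricted categories, such as related or fatal SAEs. Day 153 (1 March 2020) lies before 6 months (1 April 2020), so it is inside full collection.

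**5. Who can contribute a non-serious index event.** After dose 1 this is the Safety Subset: 350 + 350 = 700 of 5,800, or 12.1%. After revaccination it is the Revaccination Subcohorts: 2 × (120 + 135 + 120 + 120) = 990 planned, of whom 4 × 120 = 480 are in Subcohorts C and D, whose continuation is conditional (Table 1, footnote d). These are collection denominators, not expected cases.

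**The case against.** Much of the case on the other side stands.

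- **The convention can be right.** A blank end date at cut-off may mean that the event is still ongoing. A later record of the same term is then plausibly its worsening, and the earlier onset is correct. Deleting the second remark outright would split such events.
- **There is no internal contradiction.** A reader might infer that the second remark conflicts with the first. It is worded as an explicit exception, so the issue is the choice of rule.
- **Not every later event is absorbed.** A reader might infer that an open-ended AE swallows any later record of its term. Rules 1 and 4 rule that out; across periods, only the directly following non-active period is pulled into the post-dose period.
- **The SAE is not lost.** A reader might infer that it vanishes. Individual records are kept in ADaM, SAE outputs also cover the whole study period (Section 4.2.1.1), and listings or narratives are foreseen for participants with serious events (Section 4.2.1.2). What changes is the assigned onset and the period column.
- **No between-arm bias is shown.** After dose 1 the Safety Subset is balanced, the rule is the same in both arms, and safety is descriptive.

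These points narrow the scope but do not remove the defect. The rule cannot tell a truly ongoing event from a resolved one whose end date was never entered, and it treats a later SAE like any other record.

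**Conclusion.** The point holds in a limited form. An SAE that starts in the non-active period directly after a post-dose period can be reported in the 28-day post-dose tables and be missing from the follow-up column, solely because an earlier AE of the same term has no end date. In the worked example the shift is 143 days. Shifts of up to about 11 months are possible but are an edge case, because only restricted SAE categories are collected after the later of season end or 6 months.

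The number of cases cannot be estimated. It needs a post-dose AE with a completely blank end date and a later same-term SAE in the adjacent period, and the SAP gives no frequency for either. The conclusion assumes that the by-period and 28-day tables are programmed from the assigned onset and period, as rule 3 implies. The documents do not support reading 700 or 990 participants as affected, or extending the Day 153 example to the AESI interval tables.

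**What to change.** Add to the Section 4.2.1.3 remarks: where two records overlap only because an end date was imputed, a later SAE or potential AESI is not combined with an earlier non-serious record and is allocated to the period, or the Section 5.2 interval, of its own start date. The existing convention may stay for non-serious ongoing events. If the sponsor prefers to leave the combination rule untouched, the minimum is an additional tabulation of SAEs and AESIs by actual onset date.

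The cost is about two sentences in the SAP and a small change in AE programming. The downside is that a few truly ongoing conditions that become serious will be counted once in each of two periods.

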**4.2.1.4. Missing Data**

Missing data (grade, relationship) will not be imputed. Subjects who do not report an event will be considered as subjects without an event. An AE with a missing severity or relationship will be considered as an AE reported, but will be considered as not reported for the severity or relationship. For example, an AE with missing severity will be considered as an AE reported for

the analysis of any grade but will be considered as not reported for the analysis of grade 3. The analysis of solicited AEs will include the safety data as documented by the investigator.

#### **4.2.2. Vital Signs and Physical Examination Findings**

Vital signs (temperature, blood pressure, heart rate, respiratory rate, and oxygen saturation) are collected prior to vaccination and during the clinical assessment of an ARI episode for all subjects. The analysis of emerging vital sign abnormalities will be described in the clinical assessment section (Section 4.8).

Temperature will also be collected via the eDiary from vaccination until 7 days after the vaccination for Safety Subset participants. These temperatures will be allocated to predefined temperature intervals (from 37.5° C until 40°C, in steps of half degree increments; eg <37.5, 37.5-<38, 38-<38.5, ... >40) and a table will be created, showing the maximum temperatures recorded during the safety follow up of the Safety Subset participants.

Abnormalities resulting from a physical examination will either be documented as medical history or as AE. Therefore, no physical examination specific tables or listings will be generated.

### **4.3. Immunogenicity Analysis**

The analysis of immunogenicity will use the PPI set, focusing on the immunogenicity subset.

#### **4.3.1. Secondary Endpoints**

The following humoral and cellular immune responses will be measured as part of the evaluation of secondary objectives:

##### **Immunogenicity against the insert:**

###### **Humoral immune response**

- RSV A2 neutralizing titers of the vaccine-induced immune response
- Antibodies binding to RSV F protein in post-fusion and/or pre-fusion form (RSV F-protein enzyme-linked immunosorbent assay [ELISA])

###### **Cell-mediated immune response**

- ELISpot IFN $\gamma$  assay (units: SFU/10^6 PBMC). An ELISpot assay is used to quantify the amount of peripheral blood mononuclear cells (PBMCs) able to produce IFN $\gamma$  upon RSV F-protein peptide stimulation.

##### **Immunogenicity against the vector:**

- Adenovirus vector neutralization assay: This assay assesses neutralizing antibody responses against the Ad26 vectors.

#### **4.3.2. Exploratory Endpoints**

The following humoral and cellular immune responses may be measured as part of the evaluation of exploratory objectives:

**Immunogenicity against the insert:****Humoral immune response**

- RSV cross-neutralization of B strains using virus neutralization assay or other surrogate binding assays
- RSV cross-neutralization of other A strains using virus neutralization assay or other surrogate binding assays
- Functional and molecular antibody characterization: Analysis of antibody characteristics including, but not limited to, ADCC, ADCP, avidity, other respiratory viral neutralizing or binding assays, Ig Isotype, functional VNAs to other respiratory viruses, and antibody assessments for antibody repertoire.

**Cell-mediated immune response**

- Analysis of T-cell responses to RSV F protein peptide-stimulated PBMC (ICS)
- Sequencing of B-cells: including but not limited to sequencing of BCR (B-cell receptor) or VH/VL (heavy/light chain characterization) for specificity

**Immunogenicity against natural infection:**

- Antibodies binding to Ga and/or Gb protein (ELISA)

**4.3.3. Handling of Missing and/or Unquantifiable Immune Response Data**

Missing immune response data will not be imputed.

Values below the lower limit of quantification (LLOQ) will be imputed based on the type of analysis. For the calculation of the geometric mean titer or medians, values below LLOQ will be imputed to LLOQ/2. While for the calculation of the geometric mean increases, values below LLOQ will be imputed to LLOQ.

For G- Elisa ARI Day 3-5 will be treated similar to a baseline and imputation for actual values and fold rise will follow the above.

For ICS assays: the LLOQ will be used if available and validated. In case no validated LLOQ is available then a provisional cut-off will be provided before DBL (only for total cytokine response). For the individual cytokine combinations of IFN $\gamma$ , TNFa and IL2, negative values will be imputed with 0. For descriptive statistics or graphs on actual values, values below the LLOQ will also be imputed to a value of LLOQ/2.

Values above the upper limit of quantification (ULOQ) will be imputed to ULOQ.

The LLOQ and ULOQ values per assay will be available in the database.

**4.3.4. Immune Response Analysis**

No formal hypothesis on immunogenicity will be tested. Key immunogenicity assay results will also be analyzed for the subgroups defined in Section 2.4.

#### 4.3.4.1. Immunogenicity Against the Insert:

##### 4.3.4.1.1. Humoral Assays

For VNA and ELISA assays following results will be calculated: N, geometric mean§ and corresponding 95% CI of the actual values and fold increases from baseline will be tabulated and graphically presented. *§calculate the mean and corresponding 95%CI of the log2 transformed values, back-transform this mean [i.e. 2mean] and CI [i.e. 2CI].*

Actual values and fold changes from baseline are tabulated and shown as dot plots with dots for subject values, and the corresponding geometric mean and 95% CI per time point for each assay. In addition, GMT plots over time, combining the regimens in one graph (without individual subject dots) will also be created.

Ratios of actual values and of fold changes from baseline between humoral assays may also be presented.

Subject profiles of the actual values over time will be graphically presented.

Reverse distribution curves of the actual values will be provided for selected time points.

In the graphs, original values will be displayed on the log2 scale.

A scatterplot with the VNA versus ELISA will be provided for the most important time points. In these scatterplots the actual values will be shown, even if they are below the LLOQ, but the LLOQ cut-off will be visualized in the graph per assay if some values are below LLOQ.

Other exploratory parameters maybe analyzed at the discretion of the sponsor.

##### 4.3.4.1.2. Cellular Assays

For ELISpot following results will be calculated: N, median, quartiles and minimum and maximum of the actual values will be tabulated and graphically presented.

Tables with the corresponding descriptive statistics will be provided.

Subject profiles of the actual values over time will be graphically presented.

Actual values will be shown as box plots with dots for subject values, and the corresponding median and interquartile range per time point for each assay. In addition, box plots over time, combining the regimens in one graph (without individual subject dots) will also be created. For the graphs, original values will be displayed on the log10 scale.

For ICS and PBMC secreted cytokines (if available) possible analyses may include:

Total Cytokine response: the % of subsets expressing at least IFN $\gamma$ , TNF $\alpha$  or IL2 will be calculated for CD4 and CD8.

Tables with the corresponding descriptive statistics will be provided.

Subject profiles of the actual values over time will be graphically presented.

Reverse distribution curves of the actual values will be provided for selected time points.

Actual values are shown as box plots with dots for subject values, and the corresponding median and interquartile range per time point for each assay.

In addition, box plots over time, combining the regimens in one graph (without individual subject dots) will also be created.

For all cytokine combinations (IFN $\gamma$  and/or TNF $\alpha$  and/or IL2) bar charts reflecting the median magnitude of each combination will be graphically presented. Tables with the corresponding descriptive statistics will be provided.

Th1 and Th2: Th1 is defined as %RSV-F specific CD4 T-cells IFN $\gamma$ + AND/OR IL2+ and Th2 as %RSV-F specific CD4 T-cells IL4+ AND/OR IL13+ AND CD40L+. Subject profiles and graphs of the actual values over time (box-plot type) will be created. In addition, at time points of interest, scatterplots of Th1 vs Th2 might be created.

For the graphs, original values will be displayed on the log10 scale.

Scatterplot with humoral and cellular assays may be provided for the most important time points.

The technical details for the calculation of the ICS values to be used in the graphs will be outlined in the DPS.

#### **4.3.4.2. Immunogenicity Against the Vector**

For Ad26-specific VNA following statistics will be calculated: N, geometric mean§(see above for the calculation) and corresponding 95% CI of the actual values.

Actual values will be tabulated and shown as dot plots with dots for subject values, and the corresponding geometric mean and 95% CI at baseline.

Subject profiles of the assays against the insert will be repeated, highlighting subjects with pre-existing immunity at baseline against the vectors.

Scatterplots with the Adeno assay at baseline versus the assays against the inserts will be provided for the most important time points. In these scatterplots the actual values will be shown, even if they are below the LLOQ.

**4.4. EFFICACY**

**4.4.1. Analysis Specifications**

**4.4.1.1. Level of Significance**

The  $\alpha$ -levels for the primary efficacy analysis will be adjusted to:

- Account for multiple analyses. As the total number of events that will be observed is not known in advance, we will initially estimate the proportion of the total number of events ( $P_{IA}$ ) at the IA and calculate the  $\alpha$  level cut-off for the IA using ( $P_{IA}, 1$ ) as information fraction at the IA and final analysis and the Pocock rule. If the IA is not positive and the study continues, then the  $\alpha$  level cut-off at the PA will be calculated based on the  $\alpha$  spend at the IA and the IF recalculated using the actual number of events observed at the PA. The specific calculations are given below in [Table 4](#) and [Table 5](#).

And to

- Account for the multiple endpoint approach. The multiplicity correction method for the 3 primary endpoints is based on the approach by Spiessens and Debois. The exact value will be calculated based on the number of events observed for each case definition (see [Table 6](#)) at the time of analysis, targeting the same  $\alpha$ -level for each of the 3 primary endpoints using the Pocock rule.

Both methods will be combined to come to a single cut-off that will be used to define significance for each case definition. The exact significance level will depend on the number of cases already observed at the time of (interim) analysis.

[Table 4](#) and [Table 5](#) describe how the significance level (alpha) will be spend based on the possible different scenarios. In both tables, event refers to a case based on case definition 2.

**Table 4: In Case the Study is Performed at the Northern Hemisphere Only**

Number of Events at End of First RSV Season	Interim Analysis	Primary Analysis
≥ 18 events*	No interim analysis	
The Primary analysis will be conducted by the Sponsor:
 
The full alpha (<math>\alpha= 0.05</math>) will be equally divided across the 3 primary endpoints based on the observed incidence of the 3 case definitions using Pocock rule. If <math>n_1, n_2</math> and <math>n_3</math> are the number of events per CD1, 2 and 3, then the corresponding IF= (<math>n_1/n_3, n_2/n_3, 1</math>) will be used to equally divide the alpha across the 3 endpoints.

